The trial will be conducted in accordance with International Council on Harmonisation Good Clinical Practice (ICH GCP) and applicable United States (US) Code of Federal Regulations (CFR). The Principal Investigator, who in this case is also the Investigational Device Exemption (IDE) sponsor, will assure that no deviation from, or changes to the protocol will take place without prior agreement from or notification of the funding agency and documented approval from the FDA and Institutional Review Board (IRB), except where necessary to eliminate an immediate hazard(s) to the trial participants. All personnel involved in the conduct of this study have completed Human Subjects Protection and ICH GCP Training.

The protocol, informed consent form(s), recruitment materials, and all participant materials will be submitted to the IRB for review and approval. Approval of both the protocol and the consent form must be obtained before any participant is enrolled. Any amendment to the protocol will require review and approval by the IRB before the changes are implemented to the study. All changes to the consent form will be IRB approved; a determination will be made regarding whether a new consent needs to be obtained from participants who provided consent, using a previously approved consent form.

[figure not shown]
1 PROTOCOL SUMMARY

1.1 SYNOPSIS

| | |
|---------------------------|---|
| Title: | Bariatric Embolization of ArTeries with imaging visibLe EmbolicS (BEATLES) |
| Study Description: | The BEATLES study is an investigator-initiated, prospective, double-blinded, randomized, sham-controlled study that will assess the impact of bariatric embolization on the systemic levels of obesity-related hormones and, as a consequence, on weight loss. The goal of this study is to help treat obesity combining a lifestyle program and a minimally invasive, angiographic (i.e., through blood vessels) approach. |
| Objectives: | 
Primary Objective: To determine the efficacy of the BAE procedure using radiopaque 100-200 µm microspheres (BTG-001933) for weight loss in obese patients.
 
Secondary Objectives: To determine the safety and further explore the efficacy of the BAE procedure using radiopaque 100-200 µm microspheres (BTG-001933) for weight loss in obese patients
 |
| Endpoints: | 
Primary Endpoint: Change in body weight 12 months after randomization
 
Primary Safety Endpoints: All adverse events until the end of the study (12 months)
 |

| | |
|---|---|
| | Secondary Endpoints: |
| | 1) All adverse events until day 30 post embolization |
| | 2) Change in body weight at timepoints other than 12 months |
| | 3) Percentage change in body weight |
| | 4) Achievement of >5% reduction in body weight |
| | 5) Percentage excess weight loss (EWL) |
| | 6) Change in multi-compartment body fat composition as measured by MRI |
| Study Population: | 59 adult men and women, ages 21-70 years, with a body mass index (BMI) $\geq 35 \text{ kg/m}^2$ and otherwise suitable for protocol therapy at the Johns Hopkins Hospital |
| Phase: | 2 |
| Description of Sites/Facilities | 1 site: Johns Hopkins Hospital |
| Enrolling Participants: | |
| Description of Study Intervention: | Minimally invasive, non-surgical, angiographic bariatric embolization (BAE) of the left gastric and/or gastroepiploic arteries using investigational 100-200 μm radiopaque microspheres (BTG-001933, Biocompatibles UK, Ltd) |
| Study Duration: | 3 years |
| Participant Duration: | 12 months |

1.2 SCHEMA

*Will not be included in data analysis

1.3 SCHEDULE OF ACTIVITIES (SOA)

| Procedure | Pre-Procedure | Procedure Day | Follow-Up | | | | | |
|---|--------------------------------------|---------------|---|----------------------|----------------------|------------------------|------------------------|-------------------------|
| | | | 1 week (±1 day) | 2 weeks (±3 days) | 4 weeks (±3 days) | 3 months (±14 days) | 6 months (±14 days) | 12 months (±14 days) |
| Informed Consent | X | | | | | | | |
| Demographics | X | | | | | | | |
| History & Physical | X | X | X | X | X | | | |
| Study Team Visit ⁸ | X | | X | X | X | X | X | X |
| Psychological Evaluation ⁹ | X | | | | X | X | X | X |
| Blood & Urine Tests | X | X*** | X | X | X | X | X | X |
| Pregnancy Test* | X | X*** | | | | X | X* | X* |
| Stool Occult Blood Study | X | | | | | | | |
| 3D CTA | X | | | | | | | |
| Gastric Emptying* | X | | | | | X | X | |
| Endoscopy with biopsy | X | | | | | X ¹⁰ | X* | X* |
| Quality of Life Questionnaires | X | | X | X | X | X | X | X |
| Hormone Tests | X | | X | X | X | X | X | X |
| MRI | X | | | | | X | X | X |
| Weight Management Counseling (Johns Hopkins Healthful Eating, Activity & Weight Program) [†] | 8 visits over 2 months ^a | | Months 1-2: MD/WC alternating weekly, starting w/ WC; Months 3-5: MD 2x/mo; Month 6: MD 1x/mo, WC 1x/mo; Month 7-12: MD 1x/mo | | | | | |
| Randomization | | X | | | | | | |
| Gastric Meds | X | X | 6 weeks post procedure | | | | | |
| Bariatric Embolization ^{**} / Sham Procedure | | X | | | | | | |
| CT/CBCT | | X | | | | | | |
| Pain Prophylaxis | | X | AM post BAE only | | | | | |
| Assessment of AEs | | X | X | X | X | X | X | X |
| Lose It! Food Log | Start 7 days prior to first WM visit | | Subject completes food log on Lose It! application daily, reviewed at each provider WM visit | | | | | |
| ASA 24 | X | | | X | X | X | X | X |
| Hunger Satiety Scale | X | | | | X | X | X | X |
| HealthReel | X | | | | | X | X | X |
| Unblinding Survey | | | | | X | | | X |

*If applicable, e.g. in diabetic patients only (gastric emptying), female of child-bearing ability (pregnancy tests at baseline and 3 months), in case of symptoms (endoscopy in months 6 and 12), in case of endoscopy (pregnancy tests in months 6 and 12)

**Participants will be admitted to the hospital after the embolization or sham procedure.

***These labs will be performed if previous test results are >30 days old.

†Weight management schedule: weekly visits with the Johns Hopkins Healthful Eating, Activity & Weight Program during 8-week run-in and first 8 weeks post-procedure, consisting of either a visit with a physician or a weight check with a nurse. (MD: physician visit, WC: weight check)

^aWeekly visits with the Johns Hopkins Healthful Eating, Activity & Weight Program, with the following schedule: week 1: intake with provider (1 hour); weeks 2-3: weight check (15 minutes); week 4: provider follow-up visit (15 minutes); weeks 5-6: weight check (15 minutes); weeks 7-8: provider follow-up visit (15 minutes)

βStudy team visits will consist of a meeting with one of the interventional radiology fellows or study physicians as well as the study coordinators in order to check in with the patient regarding how they are doing. The post-procedural study team visits at 2- and 4-weeks post-procedure will include a physical exam.

ΔPsychology visits may be completed remotely (i.e. telehealth) if clinically indicated—this will be at the discretion of the study psychologists. Follow-up visits may be conducted more frequently than specified (i.e. optional 9-month visit).

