8.2.5 Blood, Urine, and Stool Tests

Blood tests including complete blood count, tests of liver and kidney function, serum albumin measurement, electrolytes, urea, creatinine measurements (EUC), and fasting chemistries, including glucose and insulin, will be performed at screening (and again before the procedure if the screening blood tests were done more than 30 days before the procedure) and every study visit thereafter (week 1, week 2, week 4, month 3, month 6, month 12).

A stool occult blood test to identify gastrointestinal bleeding and H. pylori blood antibody test to see if the participant has been exposed to a specific type of bacteria that can cause stomach ulcers will be performed only at screening.

All clinical laboratory assays will be performed at the Johns Hopkins CORE laboratory according to the laboratory's normal procedures. Reference ranges will be supplied by the laboratory and used to assess the laboratory data for clinical significance and out of range pathological changes. Abnormal laboratory values which are unexpected or not explained by the patient's clinical condition should be repeated until confirmed, explained or resolved. Changes from screening will be recorded as an adverse event if clinically significant.

The following clinical laboratory assessments will be completed at specified study visits during the study.

Biochemistry

- Sodium
- Potassium
- Calcium
- Blood Urea Nitrogen
- Creatinine
- Albumin
- Total Protein
- Aspartate transaminase (AST)
- Alanine transaminase (ALT)
- Alkaline phosphatase (ALP)
- Total and indirect bilirubin
- Glucose
- Lactate Dehydrogenase (LDH)
- Insulin
- Pancreatic enzymes: Amylase and Lipase

Coagulation

- Prothrombin Time (PT)
- Partial Thromboplastin Time (PTT)
- International Normalized Ratio (INR)

Hematology

- Hemoglobin
- Hematocrit
- White Blood Cell (WBC) Count
- Platelet Count
- WBC Differential and ANC
- Red Blood Cell (RBC) Count
- Mean corpuscular volume (MCV)

Lipid Profile

- Low-Density Lipoprotein (LDL)
- High-Density Lipoprotein (HDL)
- Triglycerides
- Total Cholesterol
- Total Cholesterol: HDL Ratio
- Non-HDL Cholesterol

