8.2.6 Pregnancy Test

A urine or serum beta hCG pregnancy test will be performed on all females of child-bearing potential as a part of the screening process. If the participant is a woman who is able to become pregnant, she will have a repeat pregnancy test on the day of or the day before the embolization procedure. The result of this test must be negative for her to continue in the study. Women of fertile age must agree to use birth control for the duration of the study. Pregnancy tests will also be performed within a week of endoscopies and nuclear medicine gastric emptying tests.

Pregnancy: any report of complications of pregnancy such as miscarriage or congenital abnormality recorded for any female study participant or female partner of a male study participant should be reported immediately as an SAE. Participants will be asked to use contraceptives for the duration of the study, but if they become pregnant during the study, the

participant will be removed from the study. Every effort should be made to gather information regarding the pregnancy outcome until 8 weeks post-partum. It is the responsibility of the Investigator to obtain all pregnancy information.

8.2.7 3D CTA

A 3D CT angiography will be done to check the celiac and gastric vasculature. We plan to embolize only the left gastric and/or gastroepiploic arteries.

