8.2.15 Randomization

Data documenting demographic information, medical history, physical examination, medication and prior treatment, clinical labs, pregnancy test, and urinalysis will be reviewed against the eligibility criteria to determine eligibility. The determination will be recorded on the relevant eCRF.

If a patient is determined to be eligible to participate in the study, the patient will be randomized.

Randomization will be determined using assignment by a computer-generated randomization scheme. Upon randomization/enrolment, each patient will be assigned a unique numeric patient identity code.

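### The Schedule of Activities lets a pregnancy test up to 30 days old stand on procedure day, while section 8.2.6 requires a negative test that day or the day before

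*Protocol*

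**What the plan says.** Two parts of the Protocol set the timing of the pregnancy test before the procedure.

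- **Section 1.3, Schedule of Activities (SoA).** The pregnancy row has a pre-procedure test and a procedure-day test. The procedure-day cell carries the triple-asterisk footnote: "These labs will be performed if previous test results are >30 days old". The cell directly above it, for blood and urine tests, carries the same marker.
- **Section 8.2.6.** After the screening test, a woman who could become pregnant is tested again: "she will have a repeat pregnancy test on the day of or the day before the embolization procedure". The section then makes that test a gate: "The result of this test must be negative for her to continue in the study". It gives no exception based on the age of an earlier result.

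Three other places bear on this.

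- Section 8.2.5 gives the 30-day repeat rule for blood tests, which are done at screening and "again before the procedure if the screening blood tests were done more than 30 days before the procedure".
- Section 8.1 says generally that repeat labs within 30 days of embolization are used to confirm eligibility. It does not mention pregnancy tests.
- Section 8.2.15 lists the pregnancy test among the items checked before randomization: "clinical labs, pregnancy test, and urinalysis will be reviewed against the eligibility criteria to determine eligibility". Under section 6.1.1 and the SoA, randomization takes place on procedure day.

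**The concern.** The SoA is the page that site staff are likely to work from, and section 4.4 uses it to define study completion. If it is followed as printed, a recent enough screening result removes the procedure-day test that section 8.2.6 treats as mandatory.

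Pregnancy is exclusion 15 in section 5.2. Under the SoA rule, the eligibility check at randomization can rest on a month-old result, and a pregnancy that began in between can be missed. The fetal exposure that matters is embolization with an investigational device under fluoroscopy, followed by CT. That applies to pilot patients and to women randomized to embolization. Sham participants receive sedation, local anaesthetic and a skin nick but no other procedural intervention (section 6.1.1).

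There is also a smaller cost to the data. A participant who becomes pregnant is removed from the study (section 8.2.6), and one who has already been treated is not replaced (section 7.2).

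**Working it through.** The Protocol gives no figure to reproduce here. The check sets the two rules side by side and works out when they disagree.

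**Inputs**
- SoA rule: repeat if the last result is more than 30 days old (section 1.3, footnote).
- Section 8.2.6 rule: repeat on procedure day or the previous day, whatever the age of the last result.
- Run-in: the weight-management visits are weekly "during 8-week run-in and first 8 weeks post-procedure", so 8 × 7 = 56 days.
- Other testing before the procedure: "Pregnancy tests will also be performed within a week of endoscopies and nuclear medicine gastric emptying tests". A screening endoscopy is required of everyone (section 1.3; section 5.2, exclusion 29).

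**Step 1. Where the rules disagree.** Let *a* be the age in days of the last negative test at the procedure.

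| Age of last negative test | SoA | Section 8.2.6 |
|---|---|---|
| 0 or 1 day | no repeat | satisfied |
| 2 to 30 days | no repeat | repeat required |
| more than 30 days | repeat | repeat required |

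The conflict is confined to 2 ≤ *a* ≤ 30. The largest permitted *a* is 30 days under the SoA and 1 day under section 8.2.6.

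**Step 2. Where that window falls in screening.** Assume the procedure is on day 56, at the end of the run-in. A test on day *d* is 56 − *d* days old. It is more than 30 days old when *d* < 56 − 30 = 26. A woman tested only before about day 26 is retested under both rules. A woman tested in the last 30 days is not retested under the SoA.

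**Step 3. The endoscopy-linked test.** Let the screening endoscopy be *E* days before the procedure, with its pregnancy test up to 7 days either side and no later test. The test is then between *E* − 7 and *E* + 7 days old.
- SoA never triggers a repeat if *E* + 7 ≤ 30, that is *E* ≤ 23.
- SoA always triggers a repeat if *E* − 7 > 30, that is *E* > 37.
- For *E* from 24 to 37, it depends on the test date.

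If the test is always done on or before the endoscopy day, its age runs from *E* to *E* + 7. The first limit stays at 23 days and the last falls to 30, so the uncertain band is 24 to 30 days.

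**Step 4. Is there a reconciling rule?** Section 8.2.5 confines its 30-day rule to blood tests. Section 8.1 speaks of labs in general and does not set aside the specific rule in section 8.2.6. The SoA's single-asterisk footnote names pregnancy tests at baseline and months 3, 6 and 12, and does not restore an unconditional procedure-day test. No section states an order of precedence.

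**Side point.** Section 8.2.6 also ties testing to gastric emptying scans. The SoA schedules a month-6 scan for diabetic participants, but its footnote links the month-6 pregnancy test to endoscopy alone: "in case of endoscopy (pregnancy tests in months 6 and 12".

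**The case against.** The best reply is that section 8.2.6 is specific, sound and gating. A woman treated without the test would be a breach of it, so the Protocol taken as a whole does not permit the omission. The SoA footnote says when labs will be repeated and does not forbid an earlier repeat, so a site that tests everyone on the day satisfies both texts. On this view the SoA holds a stray footnote marker copied from the row above, and required contraception (section 5.1, criterion 8) lowers the remaining risk.

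Much of this stands. The intended rule is almost certainly the one in section 8.2.6, the stricter rule can always be followed, and harm needs a site that relies on the SoA. But a footnote that makes a test conditional is naturally read as making it unnecessary otherwise, and the safeguard then depends on which page is open. Contraception and endoscopy-linked tests reduce the risk without giving the same-day or previous-day result that the Protocol chose to require.

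Two further points stand in part. The day limits in steps 2 and 3 depend on assumptions about timing, and a longer gap between screening and procedure would make a repeat under the SoA more likely. The gastric emptying point is minor: the footnote's list is introduced as examples, and section 8.2.6 already covers those scans.

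**Conclusion.** The concern holds. The SoA and section 8.2.6 give different instructions for a woman whose last negative test is 2 to 30 days old, and nothing in the Protocol resolves the difference. The maximum age of the qualifying result is 30 days under one and 1 day under the other.

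The consequence arises only where staff follow the SoA in preference to section 8.2.6. How many women fall in the window is unknown, because the endoscopy date within screening and the number of women of child-bearing potential are not stated. This is a participant-safety inconsistency that should be fixed. The planned sample size, power and type I error do not change.

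**What to change.** - In the SoA, remove the triple-asterisk marker from the procedure-day pregnancy cell. State there that the test is done on procedure day or the previous day and must be negative before randomization or, for pilot patients, before embolization. Keep the 30-day footnote for the blood and urine row.
- Add procedure day to the pregnancy-test part of the single-asterisk footnote.
- As a minor alignment, add gastric emptying scans to the condition for the month-6 pregnancy test, to match section 8.2.6.

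The main correction edits one table cell and one footnote, and costs at most one urine test per woman at a visit already planned. No analysis or sample-size text changes.

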2 INTRODUCTION

2.1 STUDY RATIONALE

The BEATLES study is an investigator-initiated, prospective, double-blinded, randomized, sham-controlled study that will assess the impact of bariatric embolization of the left gastric artery and/or gastroepiploic arteries on the systemic hormonal levels of obesity and weight loss. The goal of this study is to help treat obesity using a minimally invasive, non-surgical, angiographic (i.e., through blood vessels) approach. This Investigational Device Exemption (IDE) is requested to support the use of 100 – 200 μ m BTG-001933 microspheres in bariatric artery embolization for the treatment of obesity. The BTG-001933 microsphere (Biocompatibles UK, LTD) is an investigational device based on the legally marketed LC Bead LUMI™ (K152157, K162373), which has an approved indication for use of embolization of hypervascular tumors and arteriovenous malformations. The BTG-001933 microsphere is the result of modification of the LC Bead LUMI™ with respect to bead size range and iodine content. These device modifications may facilitate and optimize imaging techniques associated with the planned procedure.

2.2 BACKGROUND

2.2.1 STOMACH IS AN ENDOCRINE ORGAN

Although there are >40 hormones that limit food intake, there is only one hormone, ghrelin, that has been shown to be orexigenic, i.e., stimulate food intake. Discovered by Kojima et al. in the rat stomach, it has been shown to induce growth hormone release by acting on the growth hormone secretagogue receptor (GHS-R) in the hypothalamus or anterior pituitary.(1) Since the identification of this neuropeptide, extensive data in both animals and humans have shown its potent orexigenic effects.(2) Mechanisms to antagonize or suppress the effects of ghrelin on the central nervous system have resulted in dramatic weight loss and change in appetite in various studies.(2,3) In studies performed in human volunteers, intravenous ghrelin stimulates meal initiation, with nearly half of volunteers describing a sensation of hunger and a compensatory increase of 28% in caloric intake.(4) Further evaluation has shown that in humans, there is a consistent pattern of ghrelin levels rising shortly before, and falling immediately after, every meal. In situations such as weight loss, there is a compensatory increase in ghrelin levels, which may contribute to the difficulty in maintaining the lower body weight.(5) In many but not all obese participants, food fails to suppress systemic ghrelin levels, which can impair postprandial satiety and initiate overeating.(6) Due to the potent orexigenic effect of ghrelin, this hormone is a target for the treatment of obesity and weight loss. However, although various reports of ghrelin suppression have been described, none are clinically practical.

2.2.2 ANATOMY OF THE GASTRIC FUNDUS

The stomach is classically separated into seven major sections: cardia, fundus, antrum, pylorus, lesser curvature, greater curvature, and angularis (Figure 1A). While each section of the

stomach has a unique role in the digestive process, the fundus serves as the epicenter for the neuroregulatory pathway involved in satiety and appetite stimulation.(7-10) Ghrelin is expressed mainly in the fundus, which contains 10 to 20 times more ghrelin per gram of tissue than the duodenum, the next richest source, and has a higher level of growth hormone secretagogue (GHS) receptor activation than the hypothalamus.(11, 12) Notably, the vascular supply to the gastric fundus is distinct, identifiable, and can be accessed with a catheter using a percutaneous approach. The dominant flow to the fundus arises from the left gastric artery, which is the first branch off the celiac axis (Figure 1B).

[figure not shown]

Figure 1A: Anatomic drawing of the stomach. Figure 1B: Vascular supply to the different sections of the stomach.

Transcatheter gastric arterial embolization has been performed for at least three decades, and has been shown to be effective at controlling acute gastrointestinal hemorrhage. Embolization works by effectively interrupting blood flow. In addition, the gastrointestinal (GI) tract has a rich, collateral blood supply, with extensive vascular arcades that allow for safe embolization without ischemia. Thus, bariatric arterial embolization (BAE) is already a clinically viable procedure, and is currently the standard of care in participants whose condition is refractory to endoscopic control of gastrointestinal bleeding.

2.2.3 GHRELIN SUPPRESSED AFTER GASTRIC BYPASS SURGERY

More recently, ghrelin has been found to have a significant role in the long-term effect of weight loss following bariatric surgery. Since bariatric surgery isolates the gastric fundus from ingested nutrients, ghrelin profiles are shown to be lower by 77% compared to those in controls.(7,13-15) Furthermore, the normal diurnal pattern of ghrelin is interrupted, and the meal-initiated fluctuations are blunted.(7,13) Based on these findings, achieving low systemic ghrelin levels should be considered as a strategy to control obesity and maintain weight loss.

